Initial version dated: 08-20-2010

Study protocol for the Cytarabine (Ara-C) in Children With Acute Promyelocytic Leukemia (APL) (NCT01191541)

Principal Investigator

[name] MD

¹Department of Pediatrics, State Key Laboratory of Experimental Hematology and Division of Pediatric Blood Diseases Center, Institute of Hematology and Blood Diseases Hospital, Chinese Academy of Medical Sciences and Peking Union Medical College, Tianjin, China.

Eligibility criteria

Eligible patients were those who were less than 14 years old, were newly diagnosed with APL, and had not previously received chemotherapy. A molecular diagnosis was not required for enrollment, but a subsequent molecular confirmation, including the demonstration of PML-RARA transcripts, was required for inclusion in the analysis. Written informed consent was obtained from all patients before study entry.

Study design and treatment groups

The study was a prospective, randomized, single-centre trial. It was designed to determine whether the combination of ATRA and ATO is safe and effective in

paediatric APL and whether Ara-C can be omitted when ATO is added for 2 courses. Patients were assigned to receive ATRA plus ATO for induction followed by 1 consolidation course of idarubicin (IDA) and 1 consolidation course of a 28-day cycle of ATO. The patients were then randomly assigned using a computer-generated random allocation schedule to receive 2 courses of either daunorubicin (DNR) or DNR+Ara-C. Patients who were treated with DNR alone were included as the no-Ara-C group. Patients who were treated with DNR+Ara-C were included as the Ara-C group. The patients were subsequently treated with maintenance therapy consisting of oral ATRA, 6-mercaptopurine, and methotrexate for 1.5 years. When CR was achieved, all patients received a prophylactic intrathecal injection (cytarabine, methotrexate, and dexamethasone) for the first time. The patients with an initial white blood cell count $>10 \times 10^{9}$ /L then received intrathecal injection once every course. Patients with an indication of CNS leukaemia received intrathecal injection once

All children were monitored using reverse transcription polymerase chain reaction (RT-PCR) of bone marrow samples. After consolidation, the patients were assessed every 3 months for 1 year and then every 6 months for 1 year.

Criteria for response and end points

Haematological complete remission (HCR) and haematologic relapse were defined as described in previous publications. Molecular remission was defined as undetectable PML/RARa fusion transcripts. Molecular relapse was defined as the detection of the fusion oncogene PML/RARa in multiple samples within 2 weeks in the same patient. Early death (ED) was considered a death that occurred within two weeks of the beginning of treatment.

Supportive measures and management of complications

Coagulopathy was treated using fresh frozen plasma or fibrinogen. Platelet transfusions were administered to maintain a platelet count above 50×10^{9} /L until any significant sign of coagulopathy was resolved. The patients were administered hydroxyurea (1-1.5 g per day), or homoharringtonine (HHT, 1-2 mg per day for 5-10 days) when their peripheral white blood cell (WBC) counts were greater than 25×10⁹/L. At the earliest manifestation of suspected differentiation syndrome, ATRA, arsenic trioxide, or both were temporarily discontinued, and intravenous dexamethasone was administered at a dose of 5-10 mg/m² until these signs and symptoms disappeared. Antibiotics and antifungal drugs were administered for fever when required.

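### A treated child who dies with no PML-RARA result is excluded like one who tested negative, so early death could be understated and remission overstated for the ATRA+ATO aim

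*Protocol*

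**What the plan says.** Protocol, Eligibility criteria: "A molecular diagnosis was not required for enrollment", yet "a subsequent molecular confirmation, including the demonstration of PML-RARA transcripts, was required for inclusion in the analysis". The condition is a positive demonstration. The text does not separate a negative test from one that failed, is missing or was never done.

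Protocol, Study design and treatment groups, gives two aims. The first is non-randomised: "It was designed to determine whether the combination of ATRA and ATO is safe and effective" in paediatric APL. The second, whether Ara-C can be omitted, is tested by randomisation after induction, one idarubicin course and "1 consolidation course of a 28-day cycle of ATO".

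Protocol, Criteria for response and end points: "Early death (ED) was considered a death that occurred within two weeks of the beginning of treatment".

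SAP, Statistical analysis: the descriptive summaries cover the included patients, and the sample size counts evaluable patients. The SAP defines no all-treated or safety set, no handling of an absent molecular result and no related sensitivity analysis. It names EFS, DFS and OS without giving their starting points.

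**The concern.** Excluding a child who tested negative is defensible: the result describes the disease at baseline, and that child does not have the target disease. Excluding a child with no result is different, because what happens after treatment starts can decide whether a result exists. Confirmation may follow enrolment, and early death falls in the first two weeks, so death can come first and leave the test undone or unresolved.

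Such a child leaves both the numerator and the denominator. The early-death rate falls and the remission rate rises, and both shifts favour ATRA+ATO. Early death is the safety event that the Protocol defines explicitly, so one of the two stated aims is exposed. A reader of the results could not tell whether the shift was zero or material unless the exclusions were counted by reason.

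**Working it through.** **The plan's own figure.** The SAP states 31 evaluable patients per group (95% DFS in both groups, margin 14 points, 5% type 1 error, 80% power). With unpooled variance and a one-sided 5% level:

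n = 2 × 0.95 × 0.05 × (1.645 + 0.842)² / 0.14² ≈ 30 per group

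This is within one of the stated 31. The figure belongs to the randomised comparison and does not bear on this point.

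**Inputs for the illustration.** All of these are assumptions, because the documents give no counts.
- N = 66 treated: 62 (two groups of 31, from the SAP) plus 4 assumed not to reach randomisation.
- e = early deaths: 3, with 1 and 5 as the range.
- u = early deaths with no PML-RARA result: 0 to 3.
- Early deaths are taken to be the only non-remissions.

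**Formulas.**
- Early death: e/N among all treated, (e − u)/(N − u) as analysed.
- Remission: (N − e)/N among all treated, (N − e)/(N − u) as analysed.
- Both shifts have the same size, u(N − e) / [N(N − u)].

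**Results for N = 66, e = 3** (exact Clopper-Pearson 95% intervals for early death):

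| u | Early death as analysed | Remission as analysed |
|---|---|---|
| 0 | 3/66 = 4.5% (0.9–12.7) | 63/66 = 95.5% |
| 1 | 2/65 = 3.1% (0.4–10.7) | 63/65 = 96.9% |
| 2 | 1/64 = 1.6% (0.0–8.4) | 63/64 = 98.4% |
| 3 | 0/63 = 0% (0.0–5.7) | 63/63 = 100% |

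Check for u = 1: 63 / (66 × 65) = 1.5 points.

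**Range.**
- One early death of 66: 1.5% becomes 0/65 = 0%.
- Five of 66: 7.6% becomes 4/65 = 6.2%, 3/64 = 4.7% or 2/63 = 3.2%.
- Over 62 to 80 treated, 2 to 6 early deaths and 1 to 3 without a result, early death is understated by about 1.2 to 4.8 points and remission overstated by the same amount. Each excluded death taken alone (u = 1) accounts for about 1.2 points (N = 80, e = 6: 74 / (80 × 79)) to 1.6 points (N = 62, e = 2: 60 / (62 × 61)).

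**Randomised comparison.** The early-death window is 14 days from the start of treatment. Randomisation comes after induction and two consolidation courses, of which the ATO course alone is a 28-day cycle. A child who dies early is never randomised.

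**The case against.** The strongest reply is about reach and size. The SAP has one primary objective, noninferiority of the 2-year DFS rate, and early deaths do not enter it. The SAP sets no hypothesis or threshold for early death or remission, so what could move is a descriptive single-arm rate. The counts are assumed, the lower rows of the table need most or all early deaths to lack a result, and nothing in the documents suggests that. One missing result moves the rate by about 1.5 points, well inside an exact interval of 0.9% to 12.7%. All of this stands, and it limits the weight of the point. It does not remove it: the exclusion follows from the wording of the rule, and its direction is fixed.

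A second reply is that molecularly proven disease is the target population, so the confirmed set may be the main analysis, with the wider set as sensitivity. This holds fully for children who tested negative. For those with no result, either order would expose a shift, provided that the counts are reported. For a safety rate, however, an exclusion that the outcome itself can cause is the weaker default.

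A reader might also infer a bias in the DFS comparison. The rule names no confirming sample and no deadline, and "Molecular relapse was defined as the detection of the fusion oncogene PML/RARa in multiple samples within 2 weeks in the same patient", so a child with no earlier positive sample might seem to qualify for analysis only by relapsing during follow-up. The documents do not support that reading. In context, the confirmation completes the diagnosis that was not required at enrolment, and detection in follow-up has its own definition as relapse. Even if the reading is granted, the effect is small. Take 31 confirmed children per arm, m = 1, 2 or 3 more with no earlier positive result, relapse as the only DFS event, and true DFS S = 0.95. Expected analysed DFS is then 31S / [31 + m(1 − S)] = 94.85%, 94.69% or 94.54%, a drop of 0.15 to 0.46 points, with no expected difference between arms if both are at 95%.

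**Conclusion.** The point holds for the ATRA+ATO aim only. As written, the rule removes a treated child who dies with no PML-RARA result, and no other analysis set brings that child back. Any effect lowers the early-death rate and raises the remission rate, by about 1.2 to 1.6 points for one such death if 62 to 80 children are treated. EFS and OS are exposed to these lost deaths only if they run from the start of treatment, which the SAP does not state.

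The size rests on assumed counts. The documents say neither when the diagnostic sample is taken nor how many results are missing, and if every early death has a result the effect is zero. They do not show that any early death was in fact lost in this way, and that should not be inferred. The DNR versus DNR+Ara-C comparison of DFS and the 31 per group stand as they are.

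**What to change.** 1. For early death and remission, and for EFS and OS if they are measured from the start of treatment, analyse every treated child except those with a valid negative PML-RARA result. Children whose test failed, is missing or was never done stay in.
2. Report the confirmed-only set alongside as a sensitivity analysis.
3. Report the numbers positive, negative and with no result, and the early deaths in each.

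The cost is wording in the Protocol and SAP and an extra table row. Enrolment, treatment and sample size do not change. The downside is that a few children without molecular proof of APL may stay in the induction analysis, and the early-death rate may look slightly less favourable. The confirmed-only results show how much that matters.

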Statistical analysis for the Cytarabine (Ara-C) in Children With Acute

Promyelocytic Leukemia (APL) (NCT01191541)

Principal Investigator

[name] MD

¹Department of Pediatrics, State Key Laboratory of Experimental Hematology and Division of Pediatric Blood Diseases Center, Institute of Hematology and Blood Diseases Hospital, Chinese Academy of Medical Sciences and Peking Union Medical College, Tianjin, China.

Statistical analysis

The primary objective was to demonstrate the noninferiority of DNR alone compared to DNR+Ara-C in terms of the DFS rate at 2 years. Assuming a 95% rate of DFS in the two groups, a margin of -14%, 5% type 1 error, and 80% power, 31 evaluable patients per group were required to draw a noninferiority conclusion.

The characteristics of all of the included patients were summarized using cross-tabulations (for categorical variables) and quantiles (e.g., the median; for continuous variables). Nonparametric tests were used to analyse comparisons between groups (i.e., χ^2 and Fisher's exact tests for categorical variables). EFS, DFS and OS were estimated using the Kaplan -Meier method, and log-rank tests were used for comparisons. All P values were two-sided, and those with values of 0.05 or less were considered to be statistically significant. All statistical analyses were performed using SPSS software.

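### Does the lack of described stratification by initial white cell count weaken a comparison of 31 children per arm?

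*Protocol*

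**What the plan says.** The Protocol, under the heading on study design and treatment groups, states that children were "randomly assigned using a computer-generated random allocation schedule". It gives no stratification factor, block size or ratio. It does not say that none was used.

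Randomisation comes after induction, "followed by 1 consolidation course of idarubicin (IDA) and 1 consolidation course of a 28-day cycle of ATO". Initial WBC is therefore on record for every child by then. The same section singles out children with an initial count above 10×10⁹/L, who "then received intrathecal injection once every course". All children receive a first "prophylactic intrathecal injection (cytarabine, methotrexate, and dexamethasone") on reaching complete remission.

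The SAP sets the sample size: "Assuming a 95% rate of DFS in the two groups, a margin of -14" per cent, 5% type 1 error and 80% power, so that "31 evaluable patients per group were required to draw a noninferiority conclusion". For DFS it plans Kaplan-Meier estimates, and "log-rank tests were used for comparisons". No stratified or adjusted analysis is mentioned. It does plan to cross-tabulate patient characteristics and to compare categorical ones between groups by χ² or Fisher's exact test.

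**The concern.** Three facts together make this look like an oversight. The trial is small. The Protocol itself treats children differently according to a baseline count that is available before allocation. Neither the allocation nor the analysis is described as taking that count into account.

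If high-WBC children did worse and happened to cluster in one arm, the DFS difference would move for a reason unrelated to Ara-C. Because the extra intrathecal injections contain cytarabine, the arms would also differ in exposure to the drug whose omission is being tested. With few failures expected, a borderline noninferiority result could then be disputed, with no adjusted analysis planned to settle the dispute.

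**Working it through.** **Inputs.** From the SAP: 31 per arm, so 62 in all; DFS 95% in both arms; margin 14 points; type 1 error 5%; power 80%. Assumed, because the documents give neither: K = 12 to 22 of 62 children with high WBC (19% to 35%), and a 10-point DFS gap between WBC groups.

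**1. The plan's own figure.** With a one-sided 5% level, n = 2 × 0.95 × 0.05 × (1.645 + 0.842)² / 0.14² = 29.97, so 30 per arm against the stated 31. A two-sided 5% level would need 39. Sidedness is a separate matter; one-sided 5% is used below because it fits the SAP's number.

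**2. Sampling error.** SE = √(2 × 0.95 × 0.05 / 31) = 5.54 points. This is the error under unstratified allocation, so it already contains the variation due to chance imbalance in WBC or anything else.

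**3. How large imbalance gets.** In a 31:31 split the number of high-WBC children in one arm is hypergeometric, with variance 31 × (K/62) × (1 − K/62) × 31/61. The SD of the difference in shares is 2/31 times its square root:
- K = 12: 2/31 × √2.46 = 0.101
- K = 22: 2/31 × √3.61 = 0.123

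Over this range of K, a difference of at least 15 points has probability 10.6% to 28.3%, and of at least 20 points 2.2% to 10.6%. So visible imbalance is quite possible.

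**4. What it does to DFS.** The shift is imbalance × gap:
- Typical: 0.101 × 10 to 0.123 × 10 = 1.0 to 1.2 points. One child is 1/31 = 3.2 points, so this is 0.3 to 0.4 of an event.
- A 15- to 20-point imbalance: 1.5 to 2.0 points, or about 0.5 to 0.6 of an event.

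**5. What perfect balance would gain.** Write s = K/62, with failure rates f_L = 0.05 − 0.10s and f_H = f_L + 0.10. Then Var = (2/31) × [s f_H(1 − f_H) + (1 − s) f_L(1 − f_L)].
- K = 12: f_L = 0.031, f_H = 0.131; SD = √(2/31 × 0.0459) = 5.44 points
- K = 22: f_L = 0.015, f_H = 0.115; SD = √(2/31 × 0.0452) = 5.40 points

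The variance falls by 3% to 5%. Summing exactly over all outcomes, the power of the Wald noninferiority test is 82.7% unstratified and at most 83.0% with balanced arms. Simulated blocks of 4, which do not always end full, gave 81.8% to 82.3% against 82.6% to 82.8% unstratified. With no gap, the two designs are equivalent.

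**6. Where the fragility comes from.** Expected failures are 62 × 0.05 = 3.1. Wald one-sided 95% lower limits, no-Ara-C failures first:
- 2 v 1: −3.2 − 1.645 × 5.43 = −12.2 points (passes)
- 3 v 1: −6.5 − 1.645 × 6.19 = −16.6 points (fails)

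One event reverses the verdict. These limits depend only on the counts, so they are the same whether or not the allocation was stratified.

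**7. What a WBC-stratified sensitivity analysis could show.** With about three failures spread over four arm-by-WBC cells, at least one cell has no failure in 91% to 97% of trials, and two or more have none in 60% to 74%. A Greenwood variance is zero in such a cell, so the interval could be falsely narrow.

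**The case for a change.** The strongest case for stratifying is that it is nearly free. Two strata in one centre do not over-stratify 62 children, initial WBC is known in time, and blocks of 4 would hold the difference in shares to about 5 or 6 points. The cytarabine in the intrathecal injection gives WBC a link to the question under test that an ordinary covariate lacks.

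All of that stands as a reason why a designer might choose to stratify. It does not show a defect:

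- **The cytarabine link adds no separate error.** The DFS gap in the calculation is the net gap between WBC groups as treated, intrathecal injections included.
- **A larger gap changes little.** The SAP's 95% overall DFS caps the gap at 5%/share: 25.8 points at K = 12. At that extreme every failure occurs in a high-WBC child, and the balanced SD would be √(2/31 × 0.194 × 0.258 × 0.742) = 4.89 points. The gain is then real, but the case is extreme, and the unstratified test still has 82.7% power. Nothing in the documents calls a high count a risk group or shows how prognostic it remains after induction and two consolidation courses.
- **WBC above 10×10⁹/L is not the only clinical split.** The Protocol also ties intrathecal treatment to signs of CNS leukaemia, and its supportive-care section acts on a count above 25×10⁹/L.
- **Blocks carry a cost.** In fixed blocks of 4 the last allocation is always determined, and the third is when the first two agree (probability 1/3). So (1 + 1/3)/4, one third of allocations, can be deduced by anyone who knows the earlier ones.

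It is true that the SAP plans no adjusted DFS analysis. However, its comparison of characteristics between groups can show a WBC imbalance, although WBC is not named. Whether strata or blocks were used is a detail left out of a short description.

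**Conclusion.** The concern does not hold. A trial run exactly as described, with unstratified randomisation and Kaplan-Meier and log-rank comparison, gives an unbiased comparison with its type 1 error intact. Chance WBC imbalance is part of the 5.54-point standard error and not an addition to it.

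Under the assumed 10-point gap and 12 to 22 high-WBC children of 62, balancing WBC would save about 0.1 point of standard deviation and at most 0.3 points of power (83.0% − 82.7%). It would leave the dependence on single events untouched. The saving grows only if the gap is far larger, and vanishes if there is none; the documents support neither figure. Stratifying by WBC is a design preference here, and the plan needs no change on this point.

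### The comparison groups are written by treatment received, and neither document says the primary noninferiority analysis is by randomised group or what 'evaluable' means

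*Protocol*

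**What the plan says.** **Allocation.** Under Study design and treatment groups, the protocol states: "The patients were then randomly assigned using a computer-generated random allocation schedule to receive 2 courses of either daunorubicin (DNR) or DNR+Ara-C".

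**Group definition.** The next two sentences are the only definition of the groups in either document: "Patients who were treated with DNR alone were included as the no-Ara-C group" and "Patients who were treated with DNR+Ara-C were included as the Ara-C group".

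**Inclusion.** Under Eligibility criteria there is one rule: "a subsequent molecular confirmation, including the demonstration of PML-RARA transcripts, was required for inclusion in the analysis".

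**Primary comparison.** The SAP's Statistical analysis section aims to show "noninferiority of DNR alone compared to DNR+Ara-C in terms of the DFS rate at 2 years" and states that "31 evaluable patients per group were required to draw a noninferiority conclusion". It does not define the word 'evaluable'.

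**Descriptive summaries.** The SAP also says: "The characteristics of all of the included patients were summarized using cross-tabulations".

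Neither document mentions an as-randomised, intention-to-treat or per-protocol set. Neither gives a rule for a child who switches regimen, stops early or receives neither regimen.

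**The concern.** The randomisation protects the comparison only if children are counted in the arm to which they were allocated. The only written group rule uses the regimen received. Followed to the letter, it moves a switching child into the other arm and gives a randomised child who received neither regimen no group at all. The undefined word 'evaluable' leaves room for further exclusions after randomisation. If a switch or exclusion is linked to prognosis, the 2-year DFS comparison is no longer the randomised one.

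The trial is small and few failures are expected, so the status of one child can decide whether the lower limit clears the 14-point margin.

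**Working it through.** **Inputs from the SAP.** DFS is 95% in both groups, the margin is -14 points, type 1 error is 5%, power is 80%, and there are 31 evaluable patients per group.

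**Assumptions not in the documents.** All randomised children have complete 2-year follow-up, 31 are randomised per arm, and noninferiority is concluded if a one-sided 5% lower limit lies above -14 points. The SAP does not state the sidedness of the noninferiority test.

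**Step 1: the plan's own figure.** With unpooled variance,
n = [0.95×0.05 + 0.95×0.05] × (1.645 + 0.842)² / 0.14² = 29.97, so 30 per group against the stated 31. Power at 31 is 81.2%. One-sided 2.5% would need 39, which does not reproduce the figure. The one-sided 5% limit is therefore used below.

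**Step 2: how few events there are.** Expected failures per arm are 31 × 0.05 = 1.55. The margin corresponds to 31 × 0.14 = 4.3 children.

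**Step 3: examples near the margin.** These counts are chosen for illustration. Let p1 be DFS on DNR alone and p0 DFS on DNR+Ara-C.
- Wald: L = p1 − p0 − 1.645 × √[p1(1−p1)/n1 + p0(1−p0)/n0].
- Newcombe: L = p1 − p0 − √[(p1−l1)² + (u0−p0)²], where l1 and u0 are the Wilson lower and upper limits.

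For 28/31 vs 29/31, the Wald limit is −0.0323 − 1.645 × √(0.00282 + 0.00195) = −0.146.

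| Case (DNR alone vs DNR+Ara-C) | Difference | Wald | Newcombe | Result |
|---|---|---|---|---|
| 28/31 vs 29/31, as randomised | -3.23 | -14.58 | -16.17 | fails |
| 28/30 vs 29/31, one failing DNR-alone child dropped | -0.22 | -10.65 | -12.59 | passes |
| 28/31 vs 30/31, as randomised | -6.45 | -16.63 | -18.92 | fails |
| 28/30 vs 30/32, that child moved to Ara-C | -0.42 | -10.70 | -12.74 | passes |
| 27/31 vs 29/31, as randomised | -6.45 | -18.73 | -20.08 | fails |
| 27/30 vs 29/31, one failing DNR-alone child dropped | -3.55 | -15.12 | -16.81 | still fails |

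Reversal is possible but not automatic.

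**Step 4: all possible counts.** Give one DNR-alone child a DFS probability q. The other 30 in that arm follow Binomial(30, 0.95), and the Ara-C arm follows Binomial(31, 0.95). Sum the probability of every outcome in which the conclusion differs between the as-randomised data and the data with that child dropped or moved.

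| q for that child | Dropped, Wald / Newcombe | Moved, Wald / Newcombe |
|---|---|---|
| 95% | 5.9% / 2.9% | 6.3% / 3.4% |
| 80% | 7.8% / 6.5% | 9.6% / 8.6% |
| 50% | 11.5% / 13.7% | 16.0% / 19.0% |
| 0 (child fails) | 17.8% / 25.7% | 26.6% / 36.2% |

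When the child fails, every reversal goes from fail to pass. When a typical child (95%) is dropped, most go from pass to fail: 5.01 of 5.90 points by Wald and 1.61 of 2.89 by Newcombe.

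**Step 5: the opposite switch.** If an Ara-C-assigned child receives DNR alone, fails, and is counted as DNR alone, the conclusion reverses from pass to fail in 26.8% (Wald) or 39.6% (Newcombe) of trials.

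**Step 6: the price of analysing as randomised.** Suppose true DFS is 81% vs 95%, and k of the 31 DNR-alone children receive Ara-C and gain 95% DFS. The deficit becomes 14 × (1 − k/31).

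| k | Deficit (points) | False noninferiority, Wald | False noninferiority, Newcombe |
|---|---|---|---|
| 0 | 14.00 | 6.95% | 4.95% |
| 1 | 13.55 | 7.71% | 5.49% |
| 2 | 13.10 | 8.55% | 6.07% |

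**The case against.** The strongest reply is that the group sentences directly follow the randomisation sentence, so the natural reading is that they name the two arms. That is plausible, and a reader should not infer that the plan deliberately chose an as-treated analysis. But no other sentence ties the analysis to allocation, so the benign reading still leaves the rule unwritten.

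Second, the 'included' patients in the SAP can be read as those with molecular confirmation, and that sentence concerns descriptive summaries only. This stands. It does not settle 'evaluable': molecular confirmation is a disease criterion and says nothing about which arm a child counts in, or whether one who missed the randomised courses stays in.

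Third, 'evaluable' appears only as a planning count, and Kaplan-Meier estimation can retain children with incomplete follow-up. Both are true, but the method does not say who enters the analysis or in which group.

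Fourth, the large percentages need a child who is both reclassified and fails, while the plan expects only 5% to fail. They also rest on a decision rule that the SAP does not write down. This stands, and the figures for a typical child should carry the main weight.

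Finally, a reader might infer that the gap favours DNR alone. The documents do not support that: a switch in the opposite direction works against noninferiority.

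**Conclusion.** The point holds as a gap in the rule for the primary comparison. The only written group definition is by treatment received, nothing overrides it, and 'evaluable' has no meaning that can be checked. It should be fixed. Confidence is medium, because the sentences may have been intended only as labels.

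The harm is conditional on a switch or an exclusion, and the documents report neither and give no rate for either. A reader might conclude that children were moved or dropped, or that the result is biased in a known direction; the text supports neither inference.

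Given one such event in the DNR-alone arm, the conclusion reverses in about 3% to 6% of trials for a typical child. If that child fails, it reverses in about 18% to 36%, always towards noninferiority. One failing Ara-C-assigned child counted as DNR alone reverses it in about 27% to 40%, away from noninferiority. The ranges span dropping and moving (moving only for the Ara-C-assigned child) and the Wald and Newcombe limits. They assume 31 per arm, 95% DFS in everyone else, complete follow-up and a one-sided 5% limit.

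**What to change.** 1. In the protocol, define the groups as patients randomised to DNR alone and patients randomised to DNR+Ara-C.
2. In the SAP, define the primary analysis set, and the word 'evaluable', as all randomised, molecularly confirmed patients, analysed in their assigned group for 2-year DFS.
3. Add a supportive per-protocol analysis. Define its set in advance as patients who received the assigned regimen, kept in their randomised group. It answers dilution only in part, because it selects patients after randomisation, so it should not replace the primary analysis.
4. State that if the two analyses disagree, the noninferiority conclusion is reported as not robust.

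The as-randomised wording stands on its own even if the per-protocol analysis is not adopted. The cost is a few sentences, one extra analysis and possibly a more cautious conclusion. The sample-size formula and the treatment do not change. The known downside is the dilution in step 6: with one switcher, false noninferiority rises from about 7.0% to 7.7% (Wald) or from 5.0% to 5.5% (Newcombe).

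### Does intrathecal cytarabine in both arms stop the trial from answering whether Ara-C can be omitted?

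*Protocol*

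**What the plan says.** The protocol, under Study design and treatment groups, gives as one of its aims to learn "whether Ara-C can be omitted when ATO is added for 2 courses". Patients are randomised "to receive 2 courses of either daunorubicin (DNR) or DNR+Ara-C", and the arm label is then defined: "Patients who were treated with DNR alone were included as the no-Ara-C group".

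The same paragraph describes the intrathecal treatment. When CR is achieved, "all patients received a prophylactic intrathecal injection (cytarabine, methotrexate, and dexamethasone) for the first time". Patients with an initial white cell count above 10 × 10⁹/L "then received intrathecal injection once every course"; the drugs are not named again in that sentence. A further sentence on CNS leukaemia breaks off in the available text.

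The SAP, under Statistical analysis, states the primary objective as "noninferiority of DNR alone compared to DNR+Ara-C in terms of the DFS rate at 2 years". It does not mention intrathecal treatment.

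**The concern.** Read quickly, the label and the treatment do not fit. An arm named for the absence of Ara-C receives Ara-C by another route, at least once in every patient who reaches CR and perhaps repeatedly in those with a high initial count. The aim names neither route nor treatment phase.

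If the trial shows noninferiority, someone who reads only the aim and the arm name could conclude that cytarabine can be dropped altogether. The trial did not randomise that. The overreach would matter most for CNS relapse and for patients with a high white cell count, because the intrathecal treatment is heaviest there. A noninferiority design adds a further worry: if both arms receive some of the drug being removed, the visible difference between them could shrink, making noninferiority easier to show.

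**Working it through.** **1. Which comparison does the plan make?**

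| Place | What is compared or claimed |
|---|---|
| Protocol, aim | Omission of Ara-C, no route named |
| Protocol, randomisation | Two courses of DNR, or of DNR+Ara-C |
| Protocol, arm definition | No-Ara-C group = treated with DNR alone |
| SAP, primary objective | DNR alone against DNR+Ara-C, 2-year DFS |

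Three of the four rows give the same narrow contrast. Only the aim is looser, and the treatment sequence that follows it places the Ara-C in question in the two randomised courses. No two rows give incompatible instructions.

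**2. The sample size.** The SAP's calculation starts from "Assuming a 95% rate of DFS in the two groups", with a margin of 14 percentage points, 5% type 1 error and 80% power. The formula is n = 2p(1 − p)(z₁₋α + z₁₋β)² / margin². With p = 0.95 and α = 0.05 one-sided:

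n = 2 × 0.95 × 0.05 × (1.645 + 0.842)² / 0.14² = 29.97, so 30 per group.

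The SAP states 31, which is within rounding and method differences; 31 per group gives 81.2% power. With α = 0.025 one-sided the formula gives 38.04, so 39 per group, which does not reproduce 31. Which α was intended is a separate matter. The inputs are DFS rates in the two randomised groups, and nothing in the calculation depends on the arm's name or on the intrathecal schedule.

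**3. How much intrathecal cytarabine does each arm receive?**

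- Certain from the text: at least one dose for every patient who reaches CR, in both arms.
- Possible for a patient with a high initial count: 1 at CR + 1 each with the idarubicin course, the ATO course and the two randomised courses = 1 + 4 = 5. Two of the five fall in the randomised courses.
- The figure of 5 needs three assumptions: the repeat injections contain the same three drugs; every course means all four of these courses; and the injection at CR is additional to the one in the first course. The first is the natural reading, but none is stated.
- Planned difference between arms for patients with the same remission, white cell and CNS status: 1 − 1 = 0 on the certain count, and 5 − 5 = 0 on the largest count.

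**4. Does it bias the comparison?** The triggers for intrathecal treatment are CR, initial white cell count and CNS status. None is the allocated arm. It is shared background treatment, so the difference in 2-year DFS still estimates the effect of removing Ara-C from the two DNR courses on that background.

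**The case for a change.** The strongest case for acting is that the SAP does not cure the looseness of the protocol's aim. It never mentions the intrathecal cytarabine, so nothing states that a noninferior result holds only on that background. The drug being removed is also the drug in the background, which could narrow the difference. The protocol describes no stratification by white cell count, so with 31 evaluable patients per group, chance could leave one arm with more patients on repeated injections. Aligning the wording, tabulating intrathecal doses and reporting CNS relapse separately would be modest work.

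Some of this stands. The arm is not free of cytarabine, and the unqualified aim is broader than what is randomised. A report claiming that cytarabine can be dropped by every route would overreach.

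The rest does not lead to a change. The intrathecal regimen is disclosed in the same paragraph as the arm definition, so a reader has what is needed to see the condition. The documents give no data from which to size any narrowing, and an effect measured on a common background is a legitimate target. Chance imbalance in white cell count is a baseline matter, not a consequence of the label. The plan claims no result for CNS relapse or for a high-count subgroup, so a dose table and a separate CNS report would be additions that correct no wrong rule. Neither document says whether intrathecal doses are recorded patient by patient, so the table cannot be assumed to be free.

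**Conclusion.** No change is called for. The label is a defined shorthand, a little broader than its definition, and the SAP already states the comparison at the right scope. Followed as written, the plan compares DNR with DNR+Ara-C without bias from the intrathecal treatment and supports a conclusion about exactly that. Analysts will report it in those terms because those are the groups they have.

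The effect on the planned estimate, test and sample size is nil. The certain exposure is at least one intrathecal cytarabine dose per patient reaching CR, equal by plan in both arms; the figure of up to about five is conditional on the assumptions listed above.

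This conclusion assumes that intrathecal treatment was given by the stated triggers and not by arm, and that the result is reported as the contrast in the SAP's primary objective. It makes no judgement on the intrathecal schedule itself.
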